#### **Section 6.2.1 (Drug Supplies and Accountability)**

Preparation and accountability procedures for the investigational product, including those associated with home infusions whenever applicable, are described in further detail in the Pharmacy Manual.

#### **Section 6.2.4 (Dose Preparation and Administration)**

Patients must be monitored for acute allergic reactions during infusion and for at least 2 hours after the completion of the first administration of study drug at a home infusion visit or 1 hour after the completion of each administration of study drug thereafter at subsequent home infusion visits.

Epinephrine, parenteral diphenhydramine and, for infusions carried at the study site, cardiac resuscitation equipment, must be immediately available in case an allergic reaction or anaphylaxis occurs. Site personnel or professional healthcare caregiver in case of home infusions

([Appendix K](#)), must be qualified to detect allergic reactions and anaphylaxis and treat those reactions under the guidance of the PI. The home infusion personnel will be trained in basic life support (cardiopulmonary resuscitation [CPR]) but will not be required to have equipment to perform advanced life support (eg, defibrillators). See [Section 6.3.8](#) for further details regarding additional testing.

Patients should be instructed to report the development of rash, hives, pruritus, flushing, urticaria, etc, that may represent an allergic or hypersensitivity reaction to study drug. If any signs or symptoms of an allergic or anaphylactic reaction are observed during the infusion, administration of study drug must be immediately discontinued and the patient treated as appropriate. In case of home infusion, the investigator has to be notified immediately to guide treatment.

Version 1 (electronic 1.0)	07-Jul-2020	Not Applicable	Original version
Version 2 (electronic 2.0)	02-Oct-2020	Updated primary endpoint to CMH test (previously Fisher's Exact test) per feedback from FDA.	Feedback from FDA

1 INTRODUCTION

1.1 STUDY DESIGN

This is a randomized, double-blind, placebo-controlled, multicenter study designed to evaluate the efficacy and safety of BIVV009 in symptomatic patients with the complement-mediated disorder, primary CAD, who do not have a recent history of blood transfusion.

During the 6-week Screening/Observation Period, prospective patients will have a detailed medical history documented (including all available transfusion history), physical evaluations, and blood samples collected on 3 occasions approximately every 2 weeks.

The study will enroll approximately 40 primary CAD patients who do not have a recent history of blood transfusion (ie, ≤ 1 transfusion during the last year and no transfusion during the last 6 months prior to enrollment). Eligible patients should have been diagnosed with primary CAD at least 6 months prior to enrollment and should have had no history of transfusion during this period.

Eligible patients are randomized with a ratio of 1:1 to BIVV009 or Placebo by a permuted block randomization. The block size is fixed at 4. The randomization is performed by Pharm-Olam's Interactive Web Response System (IWRS). Sponsor personnel (except for those who provide drug supply) are blinded to the treatment assignment until the interim analysis (defined below).

Eligible patients will be randomized 1:1 to receive an IV infusion of BIVV009 or placebo over approximately 60 minutes on Day 0, Day 7, and every 14 days thereafter through Week 25 (ie, Days 21, 35, 49, 63, 77, 91, 105, 119, 133, 147, 161, and 175). Patients who weigh less than 75 kg will receive fixed doses of 6.5 g of BIVV009 or placebo. Patients who weigh 75 kg or more will receive fixed doses of 7.5 g of BIVV009 or placebo. Patients who miss a dose (ie, outside the dosing window or >17 days since last dose) should return to the site for an unscheduled visit 1 week prior to the next scheduled dose in order to receive an additional loading dose. Patients will have an EOT visit on Day 182 (Week 26).

During the 6-month treatment period, patients will receive a transfusion, if his or her Hgb level meets either of the following criteria:

- Hgb is <9 g/dL and the patient is symptomatic, or
- Hgb is <7 g/dL and the patient is asymptomatic.

Following completion of dosing in the 6-month treatment period, patients will continue to receive BIVV009 dosing during Part B, the long-term safety and durability of response extension phase. Part B will run for approximately one year following last patient out (LPO) under Part A.

Study primary analysis will be conducted for Part A after all patients have completed Part A and the data are cleaned. Parts A and B will have separate database locks to enable submission of the MAA following completion of Part A. Additional analyses of Part B data will be defined in a separate Part B SAP.

This statistical analysis plan contains information pertaining definitions of analysis sets and derived variables, and statistical methods for the analysis of efficacy, safety, pharmacokinetics (PK), and pharmacodynamics (PD) for Part A of the referenced study.

1.2 OBJECTIVE AND ENDPOINTS

Table 2 - Objectives and endpoints

	Objectives	Endpoints
Primary	
 to determine whether BIVV009 administration results in a ≥ 1.5 g/dL increase in hemoglobin (Hgb) level and avoidance of transfusion in patients with primary CAD without a recent history of blood transfusion. 	
 responder rate: A patient is considered a responder if he or she did not receive a blood transfusion from Week 5 through Week 26 (end of treatment [EOT]) and did not receive treatment for CAD beyond what is permitted per protocol. Additionally, the patient's Hgb level must meet the following criterion: Hgb increased ≥ 1.5 g/dL from baseline (defined as the last Hgb value before administration of the first dose of study drug) at treatment assessment timepoint (defined as mean value from Weeks 23, 25, and 26)
Secondary	
 To assess the effect of BIVV009 on clinical events and laboratory parameters related to hemolysis and anemia in patients with primary CAD To assess the effect of BIVV009 on specific complications of CAD (acrocyanosis, Raynaud's syndrome, hemoglobinuria, and thromboembolism) To assess the effect of BIVV009 on quality of life (QOL) in patients with primary CAD To evaluate the overall safety and tolerability of BIVV009 in patients with primary CAD 	
 Mean change from baseline in Hgb at treatment assessment timepoint (mean of values at Week 23, 25, and 26) Mean change from baseline in bilirubin (excluding patients with Gilbert's Syndrome) at treatment assessment timepoint Mean change from baseline in QOL, as assessed by the change in Functional Assessment of Chronic Illness Therapy (FACIT)-Fatigue scale scores at the treatment assessment timepoint Mean change from baseline in lactate dehydrogenase (LDH) at the treatment assessment timepoint Incidence of solicited symptomatic anemia at EOT Incidence of treatment-emergent AEs (TEAEs) and serious AEs (SAEs) Change from baseline in clinical laboratory evaluations Change from baseline in SLE panel Change from baseline in vital signs Change from baseline in electrocardiogram (ECG) data Physical examination findings Serum disease-related biomarkers

	Objectives	Endpoints
		
 • Incidence of hemolytic breakthrough (rapid fall in Hgb \geq2 g/dL associated with an increase in LDH/bilirubin and/or decrease in haptoglobin since the last scheduled visit) through the EOT at Week 26 • Incidence of infections of \geq Grade 3 severity (ie, requiring intravenous [IV] antibiotics) • Incidence of thromboembolic events
Tertiary/exploratory	
 • To assess the effect of BIVV009 on other quality of life (QOL) measures in patients with primary CAD • To assess the effect of BIVV009 on other laboratory parameters in patients with primary CAD • Pharmacokinetics of BIVV009 • Pharmacodynamics of BIVV009 	
 • Mean change from baseline in QOL, as assessed by the change in the five level EuroQol – five dimensions questionnaire (EQ-5D-5L) scores at the treatment assessment timepoint • Mean change from baseline in QOL, as assessed by the change in the 12-item short form survey (SF-12®) at the end of treatment assessment timepoint • Proportion of patients with Hgb level of \geq12 g/dL at the treatment assessment timepoint • Incidence of thromboembolic events after the first 5 weeks of study drug administration • Median time to normalization of bilirubin • Median time to normalization of LDH • Median time to normalization of haptoglobin • Median time to obtain Hgb level of \geq12 g/dL • Proportion of patients normalizing haptoglobin at the treatment assessment timepoint • Proportion of patients normalizing bilirubin at the treatment assessment timepoint • Proportion of patients with abnormal LDH at baseline who normalize LDH at treatment assessment timepoint • Patient’s Global Impression of Change (PGIC) to assess patient’s perception of changes in CAgD disease burden at EOT • Patient’s Global Impression of [Fatigue] severity (PGIS) to assess the patient’s perception of changes in fatigue at EOT • Incidence of disabling circulatory symptoms at treatment assessment timepoint • Total healthcare resource utilization at EOT • Plasma concentrations of BIVV009 • PK parameters: Appropriate exposure parameters (Cmax, AUC) will be derived using a population PK approach • Plasma concentrations of BIVV009 • PK parameters: Appropriate exposure parameters (Cmax, AUC) will be derived using a population PK approach

1.2.1 Estimands

Following International Conference of Harmonisation (ICH) (1) and National Research Council (NRC) (2) guidelines, the following estimands are considered for efficacy endpoints to provide clarity of what to be estimated and its connection to the trial objectives. Akacha, et al. (3) proposed a framework for defining an estimand using three attributes:

- The population of interest;
- The variable to be used for the clinical question, which consists of measurements at a specific timepoint. It could be a composite endpoint that incorporates post-randomization events.
- The measure of intervention effect, which accounts for potential effects of post-randomization events.

A composite estimand will be used for the primary endpoint and a hypothetical estimand will be used for lab parameter defined secondary endpoints. Alternative estimands are also proposed to either assist the interpretation of primary estimand or used for exploratory endpoints.

Primary estimand defined for main endpoints are summarized in below [Table 3](#). More details are provided in [Section 4](#).

For all these estimands, the comparison of interest will be the comparison of BIVV009 vs. Placebo control.

Table 3 - Summary of primary estimand for main endpoints

Endpoint Category (estimand)	Estimands			Population-level summary (Analysis and missing data handling)
	Endpoint	Population	Intercurrent event(s) handling strategy	
Primary objective: to determine whether BIVV009 administration results in a ≥ 1.5 g/dL increase in hemoglobin (Hgb) level and avoidance of transfusion in patients with primary CAD without a recent history of blood transfusion				
Primary endpoint (COVID-adjusted Composite estimand)	Responder if: 
 • Free of post-baseline transfusion within the range of Week 5 and Week 26 visit dates, and • The change from baseline in Hgb at treatment assessment timepoint ≥ 1.5 g/dL, and • Receive no protocol prohibited medications defined in Section 5.1.1 within the range of Week 	FAS	
 • Subjects who early discontinue study prior to Week 23, for reasons other than COVID-19, are considered non-responders • Subjects with no Hgb data from Week 23, 25, and 26, for reasons other than COVID-19, are considered as non-responders 	
 • odds ratio of the proportion of responders in BIVV009 and placebo, using stratified Cochran-Mantel-Haenszel test • Multiple imputation will be performed to fill in Hgb data at TAT using an MMRM approach, for subjects missing infusions at Week 23

Endpoint Category (estimand)	Estimands			Population-level summary (Analysis and missing data handling)
	Endpoint	Population	Intercurrent event(s) handling strategy	
	5 and Week 26 visit dates (excluding medications taken during a COVID-related infusion gap or within the following 5 weeks)		
 If a subject has a COVID-related infusion gap (defined as 2 consecutive missed infusions due to COVID-19), transfusions received and protocol-prohibited CAD medications taken during the infusion gap and within the 5 weeks following the infusion gap will not be included in the responder derivation. 	and 25 due to COVID-19
Primary endpoint (Composite estimand)	Responder if: 
 Free of post-baseline transfusion within the range of Week 5 and Week 26 visit dates, and The change from baseline in Hgb at treatment assessment timepoint ≥ 1.5 g/dL, and Receive no protocol prohibited medications defined in Section 5.1.1 within the range of Week 5 and Week 26 visit dates 	FAS	
 Subjects who early discontinue study prior to Week 23 are considered as non-responders Subjects with no Hgb data from Week 23, 25 and 26 are considered as non-responders 	odds ratio of the proportion of responders in BIVV009 and placebo, using stratified Cochran-Mantel-Haenszel test
Primary endpoint (Modified Composite estimand)	Responder if: 
 Free of post-baseline transfusion within the range of Week 5 and Week 26 visit dates, and The change from baseline in Hgb at treatment assessment timepoint ≥ 1.5 g/dL, and Receive no protocol prohibited medications defined in Section 5.1.1 	mFAS	
 Subjects who early discontinue study prior to Week 23 are considered as non-responders Subjects with no Hgb data from Week 23, 25 and 26 are considered as non-responders 	Odds ratio of the proportion of responders in BIVV009 and placebo, using stratified Cochran-Mantel-Haenszel test

Endpoint Category (estimand)	Estimands			Population-level summary (Analysis and missing data handling)
	Endpoint	Population	Intercurrent event(s) handling strategy	
	within the range of Week 5 and Week 26 visit dates			
Primary endpoint (Completer estimand)	Responder if: 
 Free of post-baseline transfusion within the range of Week 5 and Week 26 visit dates, and The change from baseline in Hgb at treatment assessment timepoint ≥ 1.5 g/dL, and Receive no protocol prohibited medications defined in Section 5.1.1 within the range of Week 5 and Week 26 visit 	A subset of FAS with those who complete treatment at least through Week 23 and have at least 1 evaluable Hgb from Week 23, 25, and 26	N/A	Odds ratio of the proportion of responders in BIVV009 and placebo, using stratified Cochran-Mantel-Haenszel test
Primary endpoint (Per-Protocol estimand)	Responder if: 
 Free of post-baseline transfusion within the range of Week 5 and Week 26 visit, and The change from baseline in Hgb at treatment assessment timepoint ≥ 1.5 g/dL, and Receive no protocol prohibited medications defined in Section 5.1.1 within the range of Week 5 and Week 26 visit dates 	PP set	N/A	Odds ratio of the proportion of responders in BIVV009 and placebo, using stratified Cochran-Mantel-Haenszel test
Secondary objective: To assess the effect of BIVV009 on clinical events and laboratory parameters related to hemolysis and anemia in patients with primary CAD				
Secondary endpoint (Hypothetical estimand)	Mean change from baseline in Hgb and FACIT-F Score at treatment assessment timepoint (mean of values at Week 23, 25, and 26)	FAS	
 Any value after transfusion and prohibited medication is considered missing 	Difference in mean change from baseline at TAT between BIVV009 and Placebo
Secondary endpoint	Mean change from baseline in Hgb and FACIT-F Score at treatment assessment	mFAS	
 Any value after transfusion and 	Difference in mean change from baseline at

Estimands				
Endpoint Category (estimand)	Endpoint	Population	Intercurrent event(s) handling strategy	Population-level summary (Analysis and missing data handling)
(modified hypothetical estimand)	timepoint (mean of values at Week 23, 25, and 26)		prohibited medication is considered missing	TAT between BIVV009 and Placebo
Secondary endpoint (De-facto estimand)	Mean change from baseline in Hgb and FACIT-F Score at treatment assessment timepoint (mean of values at Week 23, 25, and 26)	FAS	N/A	Difference in mean change from baseline at TAT between BIVV009 and Placebo

2 SAMPLE SIZE DETERMINATION

Approximately 40 patients with primary CAD who do not have a recent history of transfusion will be randomized. There are limited data from the published literature or available natural history data to estimate the placebo response for the transfusion-independent study population. Since patients with evidence of ongoing hemolysis, hemoglobin <10 g/dL, and symptomatic are included in the study, it is expected that few patients would meet the responder definition for the primary endpoint without treatment intervention. The proposed sample size was chosen to provide sufficient power to detect a 50% improvement for BIVV009 over a range of possible placebo responder rates with a significance level of 0.05. A total of 40 patients (20 patients per group) provides a statistical power of greater than 85% to detect a treatment difference of 50% for placebo response rates between the range of 15% to 40%. This calculation assumes a 2-sided 5%-level test comparing the response rates between the BIVV009 and placebo groups. A 50% improvement over placebo is considered clinically relevant.

3 ANALYSIS POPULATIONS

The following analysis populations are defined for Part A of the study. For the remainder of the SAP, the term “subjects” will be used to refer to patients in the study to keep consistent with the term used within table, figure, and listing (TFL) displays.

The following populations for analyses are defined:

Table 4 - Populations for analyses

Population	Description
Full Analysis Set (FAS)	The ITT population consists of all randomized subjects who received at least 1 dose (including partial dose) of study drug. All subjects in the ITT population will be included in the Full Analysis Set. Analyses of efficacy will be performed on the FAS. For analysis, FAS and the ITT population are considered exchangeable in the SAP, but the term FAS will be used in subsequent sections of the SAP and TFLs.
Modified Full Analysis Set (mFAS)	The COVID-19 pandemic occurred during the conduct of Part A study. Following the guidelines from FDA and EMA to assess any potential impact of COVID-19 on efficacy evaluation, we propose a modified full analysis (mFAS) set. The mFAS population consists of a subset of FAS who did not miss any visits or discontinue early due to the COVID-19 pandemic.
Per-protocol Set	The per-protocol (PP) population is defined as a subset of FAS who do not have any important protocol deviations impacting their efficacy assessments (defined in Section 6.3). Selected efficacy endpoints will be analyzed for the PP Population.
Safety Analysis Set	Subjects who received at least 1 dose (including partial dose) of study drug will be included in the Safety Analysis Set. Note that Safety Analysis Set is the same as FAS in this study.
PK Analysis Set	Subjects who received at least 1 dose of study drug and have evaluable PK concentrations will be included in PK analysis set.
PD Analysis Set	All subjects who receive at least 1 dose of study drug and have at least 1 evaluable PD sample during Part A will be included in the PD analysis population.

4 STATISTICAL ANALYSES

Statistical analysis will be performed by Sanofi, using SAS® version 9.3 or higher and, where appropriate, additional validated software. This SAP is based on protocol Version 6, dated 15 October, 2019.

4.1 GENERAL CONSIDERATIONS

Safety, efficacy, and PK/PD data will be summarized using standard summary statistics for continuous, categorical, and event-time data. Data will be summarized for the populations defined. All statistical hypothesis testing will be performed at the 2-sided, 5% significance level, unless specified otherwise. All p-values will be presented to 3 decimal places; p-values less than 0.001 will be presented as “<0.001,” and p-values greater the 0.999 will be presented as “>0.999.”

Unless otherwise specified, analyses will be performed by intervention group (and overall for baseline and demographics characteristics).

Continuous variables will be summarized using descriptive statistics including the number of non-missing values (n), mean, standard deviation (SD), median, minimum, and maximum. Where specified in the table shells, the 25th and 75th percentiles will also be provided. Means, medians, and the 25th and 75th percentiles will be presented to one decimal place beyond that with which the data were captured. SDs will be presented to two decimal places beyond that with which the data were captured. Minimum and maximum will be displayed to the same number of decimal places as that with which the data were captured.

Categorical variables will be summarized by counts and percentages. All percentages will be rounded to one decimal place. The percentage will be suppressed when the count is zero. Unless specified otherwise, the denominator for all percentages will be the number of non-missing data for a given summarization.

Time-to-event variables will be summarized using Kaplan-Meier estimate over time, along with median time to event and probability of an event at specific time points. Partial dates will not be imputed, hence considered unknown. In general, for subjects who do not experience the event, they will be censored at the study day of last assessment within Part A.

Part A Study Treatment Period

The Part A study treatment period starts at the date of first dose of study drug and ends at the date of Week 26 Visit if the subject completes Part A study treatment, or at the date of Early Termination (ET)/Safety Follow-up Visit if the subject discontinues the study treatment prior to Week 25.

Treatment Assessment Timepoint (TAT)

The value of an assessment (eg, Hgb) at the treatment assessment timepoint is defined as the average of the values from Week 23, 25, and 26 visits. In the case of any missing value at any of

these visits, it will be calculated as the average of the available values, unless no value is available from all three visits.

COVID-related infusion gap

COVID-related infusion gap is defined as 2 or more consecutive missed scheduled infusions due to COVID-19. For the primary endpoint analysis, transfusions and protocol-prohibited CAD medications received during a COVID-related infusion gap and within the first 5 weeks of infusion resumption will not preclude a subject from being a responder.

Solicited Symptomatic Anemia

The severity of CAD symptomatic anemia is defined in [Table 5](#). The severity grading for symptomatic anemia is adopted based on Common Toxicity Criteria for Adverse Events (CTCAE) grades and is collected in eCRFs at every visit.

Table 5 - Severity grade for symptomatic anemia related CAD

CAGD Symptomatic Anemia Term	Grade 1	Grade 2	Grade 3	Grade 4
Fatigue	Fatigue relieved by rest	Fatigue not relieved by rest; limiting instrumental ADL	Fatigue not relieved by rest; limiting self care ADL	Not defined
Weakness	Uneasiness or lack of well being	Uneasiness or lack of well being; limiting instrumental ADL	Not defined	Not defined
Shortness of Breath	Shortness of breath with moderate exertion	Shortness of breath with minimal exertion; limiting instrumental ADL	Shortness of breath at rest; limiting self care ADL	Life-threatening consequences; urgent intervention indicated
Palpitations, fast heart beat	Mild symptoms; intervention not indicated	Intervention indicated	Not defined	Not defined
Lightheadedness	Not defined	Present (eg, near fainting)	Not defined	Not defined
Chest Pain	Mild pain	Moderate pain; limiting instrumental ADL	Pain at rest; limiting self care ADL	Not defined

ADL = activities of daily living

Thromboembolic Events

The thromboembolic events prior to study entry are recorded as medical history in the eCRFs, notably pre-specified categories of TE events occurring within 1 year prior to screening are captured, while thromboembolic events on study are captured as adverse events. Both medical history and adverse events will be coded according to Medical Dictionary for Regulatory Activities (MedDRA) v20.1 (or higher).

In general, thromboembolic events may include but are not limited to:

- Any venous events
 - Portal vein obstruction
 - Deep vein thrombosis
 - Pulmonary embolism
 - Mesenteric (abdominal) venous thrombosis
- Any cerebral events
 - Cerebral infarction, occlusion, and stenosis of cerebral and precerebral arteries
 - Vascular syndromes of brain in cerebrovascular diseases, transient cerebral ischemic attacks, and related syndromes
- Any arterial events
 - Myocardial infarction
 - Mesenteric arterial thrombosis
 - Other arterial embolism and thrombosis

Medical review of medical history and AEs will ascertain thromboembolic events for analysis.

Normalization of Bilirubin

The normalization of bilirubin is defined as total bilirubin \leq upper limit of normal (ULN) (specified by the central lab).

Normalization of LDH

The normalization of LDH is defined as LDH value \leq ULN (specified by the central lab).

Normalization of Haptoglobin

The normalization of haptoglobin is defined as haptoglobin above the level of detection.

Normalization of Hemoglobin

The normalization of hemoglobin is defined as hemoglobin ≥ 12 g/dL. Hemoglobin ≥ 11 g/dL will also be investigated.

Hemolytic Breakthrough

Hemolytic breakthrough at any visit is defined as

- A decrease of 2 g/dL or more in Hgb from the last scheduled visit, and
- One of the followings:
 - An increase of LDH from the last scheduled visit,

- An increase of bilirubin from the last scheduled visit,
- A decrease in haptoglobin from the last scheduled visit.

Protocol Prohibited CAD Medications

The following concomitant medications are prohibited during the study treatment period in Part A:

- Rituximab alone or as part of combination therapy
- Cytotoxic drugs (such as fludarabine, bendamustine, ibrutinib, cyclophosphamide)
- Other investigational drugs

The efficacy endpoint (estimand) accounting for protocol prohibited CAD medication(s) use will be based on the eCRF questionnaire “Did the subject receive any prohibited medications since the last visit?” at post-baseline visits. The medical review for the list of prohibited medications will be reconciled with the eCRF questionnaire.

Pooling Sites for Analysis

Data from all investigational sites will be pooled for the analysis, unless specified otherwise.

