### 4.3.3 Exploratory efficacy endpoints (Part A)

- Mean change from baseline in QOL, as assessed by the change in the five level EuroQol – five dimensions questionnaire (EQ-5D-5L) scores at the treatment assessment endpoint
- Mean change from baseline in QOL, as assessed by the change in the 12-Item Short Form Survey (SF-12®) at the end of treatment assessment endpoint
- Proportion of patients with  $\geq 12$  g/dL Hgb at treatment assessment endpoint
- Incidence of thromboembolic events after the first 5 weeks of study drug administration
- Median time to normalization of bilirubin
- Median time to normalization of LDH
- Median time to normalization of haptoglobin
- Median time to Hgb of  $\geq 12$  g/dL
- Proportion of patients normalizing haptoglobin at treatment assessment endpoint

- Proportion of patients normalizing bilirubin at treatment assessment endpoint
- Proportion of patients with abnormal LDH at baseline who normalize LDH at treatment assessment endpoint
- Patient's Global Impression of Change (PGIC) to assess the patient's perception of changes in CAgD disease burden at EOT
- Patient's Global Impression of [Fatigue] Severity (PGIS) to assess the patient's perception of changes in fatigue at EOT
- Incidence of disabling circulatory symptoms at treatment assessment endpoint
- Total healthcare resource utilization at EOT

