4.5.1 Definition of endpoint(s)

Continuous Endpoints

The continuous endpoints include:

- Mean change from baseline in QOL, as assessed by the change in the five level EQ-5D-5L scores at the treatment assessment timepoint (TAT) and by visit
- Mean change from baseline in QOL, as assessed by the change in the 12-item short form survey (SF-12®) at the end of treatment assessment endpoint and by visit
- Mean change from baseline in hemolytic parameters (Hgb, total bilirubin, LDH, haptoglobin, and absolute reticulocyte) by visit
- Mean change from baseline in FACIT-F by visit

Response (Categorical) Endpoints

The response endpoints include (order different from protocol and not reflecting importance):

- Incidence of thromboembolic events after the first 5 weeks of study drug administration
- Incidence of CAD-related symptoms at last scheduled visit of Part A
- Total healthcare resource utilization at EOT (Part A)
- Proportion of subjects normalizing Hgb (≥ 12 g/dL) at TAT and by visit
- Proportion of subjects achieving 1.5 g/dL increase in Hgb at TAT and by visit
- Proportion of subjects normalizing bilirubin at TAT and by visit

- Proportion of subjects normalizing LDH at TAT and by visit (Proportion of subjects with $LDH \leq 1.5 \times ULN$ at TAT will also be reported)
- Proportion of subjects normalizing haptoglobin at TAT and by visit
- PGIC and change from baseline in PGIS to assess subject's perception of changes in CAgD disease burden at last scheduled visit of Part A

Time-to-Event Endpoints

Time-to-event endpoints include:

- Time to first transfusion after the first 5 weeks of study drug administration from the first dose of study drug
- Time to first transfusion (including the first 5 weeks of study drug administration) from the first dose of study drug
- For subjects who do not receive any transfusion, their time-to-event will be censored at the study day of the last scheduled visit in Part A.
- Time to first normalization of bilirubin from the first dose of study drug
- Time to first normalization of LDH from the first dose of study drug
- Time to first normalization of haptoglobin from the first dose of study drug
- Time to first normalization of Hgb level (≥ 12 g/dL)
- Time to first achieving 1.5 g/dL increase in Hgb level

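### The Part A SAP counts haptoglobin as normalized once it is detectable, so two exploratory endpoints could class below-normal values as normal

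*SAP*

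**What the plan says.** Part A SAP section 4.1 (General considerations) gives four normalization rules in succession:

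- **Bilirubin:** total bilirubin no higher than the "upper limit of normal (ULN) (specified by the central lab").
- **LDH:** "The normalization of LDH is defined as LDH value" no higher than the central laboratory's ULN.
- **Haptoglobin:** "The normalization of haptoglobin is defined as haptoglobin above the level of detection".
- **Hemoglobin:** a fixed cut-off of 12 g/dL, with 11 g/dL also examined.

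Protocol section 4.3.3 has two exploratory Part A endpoints that depend on the haptoglobin rule: "Proportion of patients normalizing haptoglobin at treatment assessment endpoint" and "Median time to normalization of haptoglobin". The synopsis and SAP Table 2 repeat them. The protocol does not say what normalization of haptoglobin means, so the SAP line is the only definition.

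SAP section 4.5.1 carries the two endpoints forward as "Proportion of subjects normalizing haptoglobin at TAT and by visit" and "Time to first normalization of haptoglobin from the first dose of study drug". The by-visit part of the first is an SAP addition.

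SAP section 4.7.3.1, on safety laboratory data, sorts results into low (under the LLN), normal (inside the range) and high (over the ULN).

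**The concern.** Being measurable and being normal are different properties. The first depends on the assay, the second on a reference population. Under the SAP's own safety vocabulary a detectable result under the LLN is low, yet section 4.1 would call it normalized. No reason is given for treating haptoglobin differently from bilirubin and LDH.

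What is at stake is the meaning of a reported result. A reader of the study report would see a proportion of patients who normalized haptoglobin, and a median time to doing so, next to bilirubin and LDH rows that do mean within the reference limit. The haptoglobin row would show only that the analyte could be measured, and its name would not reveal this.

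**Working it through.** There is no plan figure to reproduce. The check compares the rules, counts the analyses that use the haptoglobin rule, and works out which way it can err.

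**1. Rules side by side (Part A SAP 4.1)**

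| Analyte | Threshold | Kind of threshold |
|---|---|---|
| Bilirubin | at or below central-laboratory ULN | reference limit |
| LDH | at or below central-laboratory ULN | reference limit |
| Haptoglobin | above detection limit | assay limit |
| Hemoglobin | at least 12 g/dL | fixed value, shown in the protocol endpoint's name |

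Haptoglobin is the only one tied to an assay property.

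**2. Analyses that use the rule**

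- Protocol 4.3.3: two endpoints, both exploratory, both Part A.
- SAP 4.5.1: three analyses, namely the proportion at the treatment assessment timepoint, the proportion by visit, and time to first normalization.

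**3. Analyses that do not use it**

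- The primary endpoint (SAP 4.3.1) rests on hemoglobin, transfusion and prohibited medication.
- The key secondary endpoints (SAP 4.4.1.1) are changes in hemoglobin and FACIT-F.
- Hemolytic breakthrough (SAP 4.1) uses a fall in haptoglobin since the last scheduled visit.
- The continuous endpoint "Mean change from baseline in hemolytic parameters (Hgb, total bilirubin, LDH, haptoglobin, and absolute reticulocyte) by visit" uses the measured values.
- Part B treats haptoglobin as change from baseline (Part B SAP 4.4.1.1).

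**4. Direction of error**

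Let H be a patient's haptoglobin, D the detection limit and L the LLN. The plan counts H > D; a reference-range rule would count H ≥ L.

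- If D < L, everyone with H ≥ L also has H > D. In each arm: proportion under the plan − proportion under the LLN rule = share with D < H < L, which is zero or more.
- For any one patient, the first visit with H > D comes no later than the first visit with H ≥ L. Time to first normalization is therefore equal or shorter. The Kaplan-Meier median would normally follow, although censoring between the two dates means that its order is not strictly guaranteed.
- If D = L, the two rules agree apart from values exactly at the limit, and the effect is essentially nil.

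**5. Size**

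Neither document gives D, L or the distribution of haptoglobin, so the share between the limits cannot be computed. What can be stated is the weight of one patient. With 20 per group (protocol 7.10) and complete data, 1/20 = 5 percentage points of that arm's proportion. The number of such patients is unknown and may be zero.

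**6. Entry criteria**

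Protocol 5.1 limits hemoglobin and bilirubin at entry but sets no haptoglobin criterion. The protocol's LDH proportion is confined to patients abnormal at baseline; the haptoglobin proportion is not. If D < L, a patient in either arm who enters between the two limits and never changes would count as normalized throughout.

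**The case against.** The strongest reply is that the SAP states its rule openly, applies it to both arms, and contradicts nothing in the protocol, which leaves the term undefined and gives the SAP precedence (section 7). Hemoglobin also uses a threshold that is not a laboratory reference limit, so the SAP does not reserve the word for reference ranges. Detectability may be a meaningful milestone in hemolysis. Measured haptoglobin is summarized by visit in any case, and the affected endpoints are exploratory, descriptive or Kaplan-Meier summaries outside the testing sequence.

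Most of this stands, and it keeps the point small. It does not make detectable mean normal. The hemoglobin cut-off is visible in the protocol endpoint's name; the haptoglobin cut-off is not. A mean by visit does not tell a reader how many patients reached the reference range. If detectability matters clinically, that is a reason to report it under its own name.

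One part of the case against the rule also needs limiting. The low/normal/high classes in SAP 4.7.3.1 belong to safety summaries whose chemistry list does not name haptoglobin. The conflict is one of vocabulary: the SAP does not classify the same haptoglobin result in two ways.

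**Conclusion.** The point holds as a minor labelling and definition issue. It rests on one condition that the documents do not settle: that the detection limit is below the LLN and some values fall between them. Given that, the within-arm proportion is overstated by the share of patients in the gap, and individual times are shortened or unchanged. No confirmatory conclusion is touched.

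Four stronger readings are tempting but unsupported:

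- **Three protocol endpoints are affected.** The protocol has two; the third analysis is the SAP's own by-visit display.
- **Below-normal values will be reported as normal.** They could be; without either limit this is not established.
- **The overstatement has a known size.** Assuming some share of patients lies between the limits and quoting the same number of percentage points only restates the assumption.
- **The treatment effect is inflated.** The rule applies to both arms, so the between-arm difference shifts by the gap share on BIVV009 minus the gap share on placebo, which could have either sign.

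Nor do the documents say that a detectable value below the LLN shows continuing hemolysis, so the point does not rely on that.

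**What to change.** In Part A SAP section 4.1, define haptoglobin normalization as a value at or above the central laboratory's LLN. Apply it to the proportion at the treatment assessment timepoint, the by-visit proportion and the time to first normalization. Keep the present rule as a separate row named detectable haptoglobin.

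No new data should be needed: haptoglobin is in the clinical chemistry panel (protocol Appendix A), and endpoints outside the hematology panel use central-laboratory results (protocol 7.1). The cost is one SAP line and one extra row. The normalization figure may become less favourable. If the two limits turn out to coincide, the results will barely change and the label will be right.
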